#### **Exploratory Outcome Measures based on Titration Visit and Final Visit compared to Baseline Visit:**

- Bowel Management Difficulties Questionnaire – Short Form (SCI-QOL v1.0)
  - 9 multiple choice questions

Questionnaires will be administered by the research coordinator or study nurse. See Schedule of Assessments above for timing of testing.

#### **Safety Measures**

All subjects will undergo baseline blood testing, CBC and CMP. Subjects with screening estimated glomerular filtration rate (eGFR) < 60, or AST or ALT > 2x upper limit of normal will be excluded. At screening, subjects reporting dysuria, fever or abdominal pain will undergo urine analysis, culture and sensitivity at the discretion of the principal investigator. Subjects with blood pressure > 165 systolic or 100 diastolic will be excluded at screening or discontinue study medication if this occurs while on study medication. However, they may complete other elements of the study. Subjects with screening post-void residual > 200ml will be excluded. Symptoms of urinary retention will be monitored throughout the study and may lead to early discontinuation of study medication; however, such subjects may complete other elements of the study. Subjects with a range of health conditions that may put the patient at risk for adverse outcomes will be excluded, as listed under Exclusion Criteria. Female subjects will undergo urine pregnancy testing if they are deemed to have any risk of being pregnant or becoming pregnant during the study.

Subjects will be monitored for adverse events throughout the trial. The occurrence of adverse events will be ascertained by observation, telephone monitoring and questioning by the investigator. Safety assessments will consist of monitoring and recording all adverse events, including serious adverse events.

Adverse events include adverse drug reactions, illness with onset during the study, exacerbations of pre-existing conditions or clinically significant changes in physical examination or significantly abnormal objective test findings. Medical conditions/diseases

---

present before starting study treatment are only considered adverse events if they worsen after starting study treatment. All adverse events will be recorded and graded as mild, moderate or severe by the principal investigator in accordance with general guidelines of clinical research. The principal investigator and all other research staff will be blinded towards randomization of active drug versus placebo until after completion of study.

Adverse events that arise between the Baseline Visit and Final Visit will be classified as acute therapy phase adverse events.

A serious adverse event is an undesirable sign, symptom or medical condition which: 1. is fatal or life-threatening, 2. required or prolonged hospitalization, 3. results in persistent or significant disability/incapacity, 4. constitutes a congenital anomaly or a birth defect, 5. is medically significant, in that it may jeopardize the subject and may require medical or surgical intervention to prevent one of the outcomes listed above. If any serious adverse events occur, the treatment status of the subject(s) may be revealed, as clinically indicated. Subjects who discontinue medication use will be followed for adverse events until reaching the termination of adverse events. No interim analysis of safety data is planned because the entire study will be conducted over 2 months. However, the frequency of adverse events (AE) will be under continuous scrutiny during the observation with comparison to AE rates that have been recorded in published MS fatigue drug trials.

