STUDY SUBJECTS	40 subjects with multiple sclerosis and OAB complaints.
DESIGN	Multiple-dose, randomized, placebo-controlled prospective, single-site, investigator-initiated trial.
DURATION OF STUDY	Approximately 10 weeks (active treatment)

TREATMENT REGIMEN	
Group A will receive Mirabegron 25mg daily      Group B will receive placebo      Group A and B will receive the same baseline education in pelvic floor exercise based on viewing of an instructional presentation plus take-home printed material.

TRIAL PERIODS	
Screening Period
 
 
• Screening to Baseline
 
 
Treatment Period
 
 
• Baseline to Final Visit (or Study Drug Discontinuation), includes Baseline, Phone Visit 1, Titration Visit, Phone Visit 2 and Final Visit
 

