## Background

There are 400,000 Americans with MS and past and current surveys indicate that more than 80% report some bladder dysfunction, including 61% with urinary urgency. In MS, immune dysregulation and neurodegeneration in the central nervous system impairs normal micturition. Symptoms include frequency and/or urgency of urination, hesitancy in starting urination, nocturia and incontinence. Urological studies have shown the most common complaint is urinary urgency due to overactive bladder (OAB), with urinary retention less common. This is supported by urodynamic findings of detrusor hyperreflexia in 68% of a MS cohort. One study suggests that detrusor hyperreflexia is more severe when related to MS than when idiopathic. Urinary urgency and urge-incontinence symptoms have markedly negative impacts on physical functioning and mental-functioning health-related quality of life metrics in MS.

Potential treatments for OAB include behavioral modification, pelvic floor rehabilitation, oral or intravesical anticholinergic medications, desmopressin, duloxetine, intravesical injection of botulinum toxins, medicinal cannabis, or placement of external or indwelling catheters. Mirabegron (MBG) is the first beta-3 adrenergic agonist drug indicated for OAB treatment with symptoms of urge urinary incontinence, urgency and urinary frequency (see prescribing information). This was based on studies conducted in general populations having OAB symptoms and not stress incontinence. MBG has not been studied in MS.

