**Early Termination**

Criteria for early termination include, but are not limited to < 36 hours of time covered in a bladder diary, poor adherence to study medication (less than 70% of study medication consumed), safety issues related to study-related or non-study related adverse events, and at the request of the subject or at the discretion of the investigator.

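### The only running check on adverse event rates uses MS fatigue drug trials as its yardstick, which is the wrong comparator for a bladder drug

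*Combined protocol and SAP*

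**What the plan says.** The Safety Measures section handles safety mainly subject by subject. Adverse events are found in a general way: "The occurrence of adverse events will be ascertained by observation, telephone monitoring and questioning by the investigator". All of them are to be recorded and graded. Blood pressure has a numeric limit (165 systolic or 100 diastolic), above which subjects "discontinue study medication if this occurs while on study medication". For retention the wording is discretionary: "Symptoms of urinary retention will be monitored throughout the study and may lead to early discontinuation of study medication".

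At the level of the whole trial, the same part of the protocol rules out an interim safety analysis, on the ground that the study will last two months. It then says that adverse event frequency will be kept under continuous scrutiny, with "comparison to AE rates that have been recorded in published MS fatigue drug trials". The principal investigator and other research staff are to stay blinded until the study is complete.

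The Background cites three mirabegron trials (references 16-18) and says they were done in general populations with overactive bladder symptoms. Sample Size Considerations makes safety in this population a purpose of the study and argues that too few subjects could miss a common safety issue.

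**The concern.** A running comparison with outside rates is useful only if those rates say what to expect of this drug in this condition. Fatigue drug trials test different agents for a different complaint. An excess of retention or raised blood pressure would have no relevant expected rate to stand out against, and an unremarkable comparison would give unearned reassurance. The mismatch matters more here because nothing else in the text examines accumulating rates before unblinding.

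Retention shows the problem most clearly. The plan treats it as a possible reason to stop drug, and the Background describes MS bladder disease this way: "Symptoms include frequency and/or urgency of urination, hesitancy in starting urination, nocturia and incontinence". Some subjects may therefore have voiding difficulty before their first dose, and conditions "present before starting study treatment are only considered adverse events if they worsen after starting study treatment". Recognising worsening is easier if the same named symptoms were asked about before treatment.

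**Working it through.** The plan gives no figure to reproduce on this point. The check sets its provisions side by side.

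1. **Safety provisions during the trial.**
   - Individual level: adverse event assessment at all four on-treatment contacts; the blood pressure limit; discretionary stopping for retention; Early Termination for adverse event safety issues or at investigator discretion; Unscheduled Visits; and a prompted visit for a possible MS exacerbation (Serious Adverse Events Reporting).
   - Aggregate level: no interim analysis. Comparison by arm is closed to blinded staff. The research pharmacist and unblinded dispensing staff know assignments (Randomization), but the text gives them no safety review role. Comparison with fatigue trials is what remains, so there is one aggregate check.

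2. **How long it is relied on.** The Final Visit falls on days 74-82, or 74/7 = 10.6 to 82/7 = 11.7 weeks, so one subject's follow-up already exceeds two months. Study Timeline in the Protocol Summary allows 22 months of enrollment. The check therefore serves for far longer than the stated reason implies.

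3. **What a blinded comparison needs.** With 20 subjects per arm, the expected pooled proportion with an event is (20 × p_drug + 20 × p_placebo)/40 = (p_drug + p_placebo)/2. Judging an excess requires an expected value of p_drug for mirabegron. Fatigue drug trials cannot supply one. Mirabegron overactive bladder trials can in principle, for a non-MS population.

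4. **Where named questions could go.** The treatment period "includes Baseline, Phone Visit 1, Titration Visit, Phone Visit 2 and Final Visit". The windows, in days after randomization, are Phone Visit 1 at 28-32, Titration at 35-40, Phone Visit 2 at 70-74 and Final at 74-82. Each contact, and Baseline, already lists an adverse event assessment. At the Titration Visit this sits alongside the dose choice, so a named enquiry and a hold on up-titration need no new contact.

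5. **What the questions would not change.** First dose to first planned contact stays 28-32 days. Titration to Phone Visit 2 stays 70 − 40 = 30 to 74 − 35 = 39 days, or up to 74 − 32 = 42 days with the 32-40 day window in the Background.

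**The case against.** **On the benchmark.** The best defence is that the placebo arm, not outside rates, will show whether an event is more frequent on drug. That is right for the final analysis but gives no help while staff are blinded. A second defence is that fatigue trials at least enrol people with MS and may show background rates in that disease, whereas references 16-18 do not. This stands in part: neither source matches both drug and disease, and the documents do not show whether the cited trials report retention. It is a reason to state the limitation, not to keep a comparator that says nothing about mirabegron.

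**On retention.** Much of the case against asking for more is sound. Clinical judgement by a blinded investigator is an ordinary way to handle a symptom, and a numeric limit like that for blood pressure is not to be expected. The 50 mg choice is made in consultation with the investigator, at a visit that already includes adverse event assessment and diary review. What is missing is an explicit sentence, so the named enquiry is an improvement and not the repair of an error.

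**Stronger readings that a reader might infer.**
- *Retention counts by arm depend on how sites read the discretionary stopping phrase.* They do not. That phrase governs stopping drug; recording all adverse events is required separately.
- *There is no starting point before drug.* The Screening Visit includes an ultrasound residual, history and examination, and Baseline includes an adverse event assessment. Named questions would sharpen this starting point, not create it.
- *No contact asks about retention.* This cannot be established. The questionnaire items, Appendices 1 and 2 and the consent text were not available, and the visit lists name assessments, not interview items.

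**Conclusion.** The benchmark is wrong as written and should be changed. It is the only aggregate safety check described during the trial, it applies to all 40 subjects, and it cannot serve its purpose for a bladder drug. The conclusion rests on the supplied text; a separate safety plan, if one exists, could alter it. The effect is on safety oversight and interpretation, not on the primary efficacy analysis.

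The retention enquiry is secondary: worthwhile because it is nearly free and the plan itself links these symptoms to stopping drug. A reader might go further and estimate how many retention cases would be missed. The documents give neither an event rate nor the share of cases general questioning would find, so such an estimate would be assumption only. Nor should the enquiry be presented as closing the intervals of about a month between planned contacts, because it adds no contact.

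**What to change.** 1. **Benchmark (correction).** In the adverse event paragraph of Safety Measures, replace the reference to MS fatigue drug trials with adverse event rates from the mirabegron overactive bladder trials already cited (references 16-18). State that these are not MS populations, and take rates at comparable exposure where reported: the title of reference 16 describes a 12-month study, against 74-82 days here.
2. **Reporting.** State that retention events will be reported by arm after unblinding.
3. **Named enquiry (improvement).** Ask a few retention symptoms yes/no, for example hesitancy, weak stream, incomplete emptying and inability to void, at Baseline before drug and within the adverse event assessments already listed at Phone Visit 1, Titration, Phone Visit 2 and Final.
4. **Dose step (improvement).** Add to the Titration Visit that a subject with a new or worse symptom under blinded investigator review is not up-titrated until the review is complete.

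The cost is a few sentences and a short question set at contacts that already exist. No visit, routine scan, residual limit or committee is added. The downside is that asking by name will raise reported symptom counts somewhat in both arms; since both are asked alike under blinding, the comparison between them stays fair.

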### **Serious Adverse Events Reporting**

The FDA will be informed of serious unexpected adverse reactions (SAEs) as soon as possible or within 15 calendar days. In addition, the Investigator will notify the FDA of any unexpected, fatal or life-threatening experience associated with the use of the drug as soon as possible, or within 7 calendar days, by telephone or facsimile. When the principal investigator has determined that a Serious Adverse Event requires reporting to the FDA (unexpected and possibly related to study drug), the following actions will be taken:

1. Telephone the FDA immediately (day of awareness), in the case of reportable death or life threatening events.
2. Complete FDA Form 3500.
3. Send the completed Form 3500 to the FDA (preferably by fax at [name]) within the timelines mentioned above.
4. Attach the photocopy of all examinations, medical notes and records related to the Serious Adverse Event and document the dates these were made. For laboratory results, include the laboratory normal ranges. For hospitalizations, Admission H&P, Discharge Summary, Consultative reports, etc. could be very helpful. In the case of a fatal event, provide an autopsy report, when it becomes available.

Any symptoms or signs that could be due to an MS exacerbation will prompt an unscheduled visit with the investigating physician to confirm or refute an MS exacerbation. Any confirmed exacerbations will be noted in the results, but will not lead to removal from the study unless it is deemed by the subject or the investigating physician to be in the subjects' best interest to do so. Treatment of exacerbation with IV methylprednisolone 1gm daily for three days with oral steroid taper may be provided at the investigator's discretion.

## Sample Size Considerations

This is a prospective double-blinded, controlled pilot study. The purpose is to test a hypothesis in a preliminary fashion and to assess for safety in this population with a specific neurological disease. As such, a power calculation may be irrelevant. However, a small number of subjects (e.g.) less than 10, may cause significant sampling error to miss a treatment effect or common safety issue. Some entities that establish criteria for level of evidence consider a sample size of 20 subjects in each arm to be a minimum representative population to be considered for Class III or better classification of Level of Evidence. Therefore, a sample size of 40 subjects is a reasonable number for a pilot study of this nature.

## Statistical Analysis

Demographics and baseline disease characteristics, including age, gender, MS type and duration of disease, level of disability (EDSS), and disease modifying therapy status will be compared between study groups.

Summary and analysis of primary and secondary outcome measures will include

1. Summary statistics (n, mean, standard deviation, median, minimum and maximum) at baseline and week 5 and week 10 by treatment
2. Summary of % change from baseline to week 5 and 10.
3. Significance testing

For the primary outcome measure, Average daily OAB-SCS, each voiding event is multiplied by the score for the event and then all events are summed to generate a total daily OAB-SCS cumulative score. Each daily total score is averaged to generate the Average daily OAB-SCS total score. For incomplete days (e.g. went out for 6 hours and forgot to record voids) the sum score will be adjusted as follows: total score over 24 hours X 24 / actual # of hours included in documentation (see reference Zinner et al).

Mean OAB-SCS score at Baseline Visit will be included in the model as an independent variable. The primary time points for all comparative measures will be Baseline Visit, Titration Visit and Final Visit. Outcome measures will be compared between groups using analysis of covariance (ANCOVA) or other method. Demonstration of superiority will depend on achieving statistical significance for the primary endpoint. Level of significance will be defined as  $p=0.05$ . All statistical tests will be two-sided. Statistical assistance will be provided by a statistician consultant whose company is contracted with EvergreenHealth and whose services we have used on two recent MS studies.

Aggregate, de-identified data from the Bladder and Bowel Management Difficulties Short Form Questionnaires (SCI-QOL v1.0) will be shared with the University of Washington in Seattle, WA. This will be done as a courtesy for giving the investigator permission to use these questionnaires in this protocol.

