### **Interruption or discontinuation of treatment**

Every patient has the right to discontinue study participation at any time, and every patient may be discontinued from the study by the PI for any reason beneficial to his/her wellbeing or any other reason. All data generated up to the time of discontinuation from the study will be analyzed and the reason(s) for discontinuation will be recorded.

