**Efficacy Assessment****Primary Outcome Measure**

Average daily OAB-SCS total score based on OAB SCS at Final Visit vs. Baseline Visit. Every toilet void or incontinence episode will be recorded in a diary based on the OAB-SCS system: 1 = no urgency (normal voiding); 2 = mild (could postpone voiding for as long as necessary without fear of incontinence); 3 = moderate (could postpone voiding for a short while without fear of leakage); 4= severe (could not postpone, had to rush to the toilet); 5= urgency incontinence (could not make it to the toilet without some leakage). Every incontinence episode is scored as 5. Each voiding event is multiplied by the score for the event and then all events are summed to generate a total daily OAB-SCS cumulative score. Each daily total score is averaged to generate the Average daily OAB-SCS total score. For incomplete days (e.g. went out for 6 hours and forgot to record voids) the sum score will be adjusted as follows: total score over 24 hours X 24 / actual # of hours included in documentation (see reference Zinner et al).

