**Secondary Outcome Measures based on diaries compared to Baseline Visit:**

- Average daily OAB-SCS total score based on OAB SCS reviewed at Titration Visit
- Titration Visit and Final Visit mean number of micturition/day\*
- Titration Visit and Final Visit mean number of incontinence episodes/day\*
- Titration Visit and Final Visit mean volume voided/micturition\*

\*missing blocks of time will not be included in the scoring

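### The primary analysis has no rule for a missing Final Visit score; a pre-specified repeated-measures model would bring leavers' Titration diaries into the primary test at little cost

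*Combined protocol and SAP*

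**What the plan says.** The Primary Outcome Measure section sets the comparison: "Average daily OAB-SCS total score based on OAB SCS at Final Visit vs. Baseline Visit". The Statistical Analysis section gives the method: "Outcome measures will be compared between groups using analysis of covariance (ANCOVA) or other method". It adds "Mean OAB-SCS score at Baseline Visit will be included in the model as an independent variable" and "The primary time points for all comparative measures will be Baseline Visit, Titration Visit and Final Visit", without saying whether the visits are analysed jointly or one at a time. Superiority rests on the primary endpoint at a two-sided 0.05 level.

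The only missing-data rule for this score scales an incompletely recorded day up to 24 hours. No analysis population, imputation, repeated-measures model or sensitivity analysis is given for an absent Final score.

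Three other places bear on the point. The section on interruption or discontinuation of treatment states "All data generated up to the time of discontinuation from the study will be analyzed and the reason(s) for discontinuation will be recorded". The diary-based secondary outcomes include "Average daily OAB-SCS total score based on OAB SCS reviewed at Titration Visit". The Safety Measures section says of subjects who stop drug because of urinary retention symptoms that "such subjects may complete other elements of the study", and it says much the same for a blood pressure stop. Stopping drug is therefore not the same as having no Final diary.

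**The concern.** An ANCOVA of the Final score uses only subjects who have one. A subject who completes the Titration diary and then leaves contributes nothing to the primary test, so the general statement that data up to discontinuation will be analysed is met for that subject only through the week 5 secondary outcome.

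Two things are at stake. The first is information: the Titration score predicts the Final score and is already collected. The second is bias: if subjects with poor Titration scores leave more readily in one arm than in the other, the remaining completers are no longer comparable. With 20 per arm, a loss of 10-25% is two to five subjects per arm.

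The open alternative to ANCOVA adds a further weakness, because the method could be settled after the data are seen.

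**Working it through.** **Inputs from the documents.** 40 subjects, 20 per arm; two post-baseline diaries (Titration, Final); baseline as covariate; two-sided 0.05. There is no power calculation to reproduce. Loss rates, correlations, effects and loss mechanisms are not given, so all are assumptions below. Scores are in SD units and higher is worse.

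**Where the leaver's diary enters.** Let A be arm, B baseline, T the Titration score and F the Final score, with some F missing.

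- Completers' ANCOVA: regress F on B and A in subjects who have F. The effect is the coefficient of A. T is not used.
- Repeated-measures maximum likelihood (unstructured covariance, baseline-by-visit terms, loss only after Titration): regress T on B and A in everyone, giving h for arm. Regress F on B, A and T in completers, giving g_A and g_T. The effect at Final is g_A + g_T × h. Leavers enter through h. With complete data the two estimates coincide.

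**Simulation 1.** 20 per arm; correlations B-T 0.55, B-F 0.50, T-F 0.60 to 0.75; benefit 0 at both visits, or 0.5 SD at Titration and 0.6 SD at Final; loss 10-25% per arm.

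| Loss after Titration | Bias of completers' ANCOVA (SD) | Excess MSE of ANCOVA over repeated measures |
|---|---|---|
| Random | about 0 | 1-11% |
| Follows Titration score alike in both arms | about 0 (at most 0.012) | 2-7% |
| Follows Titration score in placebo only | 0.04-0.16, against mirabegron | 3-35% |

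Against a 0.6 SD effect, the last row is 0.04/0.6 = 7% to 0.16/0.6 = 27%. The standard error is about 0.29-0.33 SD under either method, so the largest bias is about half a standard error. In the last row the repeated-measures estimate stayed within about 0.01 SD of the truth.

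The ranges depend on how steeply loss follows the score. A repeat with logistic loss (slope 1.5 or 2.5 per SD, 6,000 runs per setting) gave a bias of 0.03-0.18 SD in the placebo-only case. In the alike-in-both-arms case it gave an MSE ratio of 0.97-1.05, so there the gain can be nil.

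**Simulation 2, including loss that is not at random.** 20 per arm, 6,000 runs; benefit 0.3 SD at Titration and 0.5 SD at Final; a common correlation of 0.5 or 0.7. Loss is 20% per arm when random, otherwise 20% in placebo and 13% (random) in mirabegron.

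| Loss in placebo | Correlation | ANCOVA bias (SE) | Repeated-measures bias (SE) |
|---|---|---|---|
| Random | 0.5 | 0.001 (0.311) | 0.000 (0.309) |
| Random | 0.7 | -0.002 (0.262) | -0.002 (0.258) |
| By observed Titration score | 0.5 | 0.056 (0.302) | -0.001 (0.304) |
| By observed Titration score | 0.7 | 0.048 (0.253) | -0.004 (0.252) |
| By unobserved Final score | 0.5 | 0.176 (0.291) | 0.157 (0.289) |
| By unobserved Final score | 0.7 | 0.124 (0.251) | 0.104 (0.249) |

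Where loss follows the unobserved Final score, the share of bias remaining is 0.157/0.176 = 89% and 0.104/0.124 = 84%.

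**What the model estimates for leavers.** It predicts a leaver's Final score from completers in the same arm. If mirabegron leavers in fact lose a 0.6 SD benefit (assumption), the effect over all randomised subjects is overstated by 0.6 × 10% = 0.06 to 0.6 × 25% = 0.15 SD. The plan has to say which effect it wants.

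**The case against.** Three stronger readings are tempting, and the documents support none of them.

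- *The plan cannot use the Titration diary, and contradicts its own statement on discontinued subjects.* It leaves another method open and lists Titration among the primary time points, so a repeated-measures model is allowed. The statement on discontinued subjects does not say that every value enters the primary test, and a leaver's Titration score is analysed as a secondary outcome. The gap is one of specification.
- *The completers' ANCOVA is biased.* It is so only if loss relates to outcome differently in the two arms. No passage establishes that. Both arms are offered blinded up-titration at the Titration Visit, which gives a subject doing poorly a reason to stay, and subjects who stop drug for blood pressure or retention may still supply a Final diary.
- *A repeated-measures model removes the bias.* It does so only if arm, baseline and Titration score explain the loss. The early termination criteria include adverse events, poor adherence and subject request, all of which can arise after the Titration diary.

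It is also fair to say that this is a 40-subject pilot, that the gain is small in most scenarios, and that other missing-data methods would serve. What stands is that the plan ties a superiority claim to this test without fixing its method, its population or its handling of a missing Final score.

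**Conclusion.** The point holds as a cheap improvement. The plan has no rule for a missing Final score, and a single-visit ANCOVA without imputation would leave the Titration diaries of later leavers out of the primary test. At an assumed 10-25% loss, the cost ranges from almost nothing (random loss, or loss alike in both arms) to a bias of about 0.04-0.16 SD and up to 35% excess mean squared error (loss tied to the Titration score in one arm). These sizes rest wholly on assumed rates, correlations and mechanisms. The repeated-measures model lowers this risk but does not abolish it, and it adds nothing for subjects who leave before the Titration Visit.

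**What to change.** In the Statistical Analysis section, for the primary endpoint:

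1. Delete the open alternative to the named method. Specify a repeated-measures mixed model of average daily OAB-SCS at Titration and Final, with arm, visit, arm-by-visit, baseline and baseline-by-visit terms, unstructured covariance and Kenward-Roger degrees of freedom.
2. Define the population as all randomised subjects with a baseline and at least one post-baseline diary.
3. Make the arm difference at the Final Visit the single primary contrast at two-sided 0.05. The Titration contrast from the same model serves the existing secondary outcome.
4. State the effect being estimated for subjects who stop study drug, including whether diaries recorded after the stop are used.
5. Keep the completers' Final Visit ANCOVA as a sensitivity analysis, and add one for loss that is not at random, for example a delta adjustment.

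The cost is statistical wording and a little more programming, with no new data, visits or subjects. The downside is reliance on a missing-at-random assumption that cannot be tested, which is why the last sensitivity analysis is needed.
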